9.3.2 Authorized Therapy

Combined with the intake of a study product, by decision of a study physician; the following products for the symptomatic treatment of acute respiratory infections may be prescribed to this study subjects:

- Ascorbic Acid (Vitamin C)
- Adrenomimetics (intranasal)
- Antipyretic agents at temperatures above 38.5 °C (Efferalgan®).
- Expectorant drugs (Codelaс Broncho)
- Mucolytic drugs (Acetylcysteine)
- Fenspirid

Information about the antipyretic used in this study is provided below.

Trade name: Efferalgan®

International non-proprietary name Paracetamol

Pharmaceutical form: oral solution [for children]

Composition:

100 ml of the product contains:

Active ingredient: paracetamol 3.000 g

Excipients: macrogol 6000 - 20.000 g; sugar syrup (sucrose, water) - 50.000 g; saccharinum naticum - 0.150 g; potassium sorbate - 0.400 g; caramel vanilla flavoring* - 0.200 g; citric acid - 0.107 g; purified water - up to 100 ml.

* *Composition of caramel vanilla flavoring:* butanedione, acetylmethyl carbinol, benzaldehyde, propylene glycol, gamma heptalactone, benzyl alcohol, triacetin, piperronal, amyl cinamate, vanillin, acetyl vanillin.

Appearance

Brown slightly viscous solution with caramel-vanilla smell.

Pharmacotherapeutic group: analgesic non-narcotic agent.

ATC code: N02BE01.

Pharmacological properties

(Na⁺ and water retention) and mucosa of the gastrointestinal tract.

Pharmacokinetics

Paracetamol absorption after oral administration is complete and rapid. Maximum plasma concentration is reached in 30-60 minutes after administration. Paracetamol distribution in tissues occurs rapidly. Distribution volume in children is 0.7-1.01 l/kg.

Indications for use

Efferalgan® is used in children from the age of 1 month to 12 years (with a body weight of 4 to 32 kg) as an antipyretic for acute respiratory diseases, flu, childhood infections, post-vaccination reactions and other conditions accompanied by fever.

The drug is also used as an analgesic for pain syndrome of weak or moderate intensity, including: headache, toothache, muscle pain, neuralgia, pain in injuries and burns.

Contraindications

- hypersensitivity to paracetamol, propacetamol hydrochloride (paracetamol prodrug) or other components of the drug;
- severe liver dysfunctions or decompensated hepatic disorder at the active stage;
- aged up to 1 month;
- Sucrase/isomaltase deficiency, fructose intolerance, glucose-galactose malabsorption.

With caution

Severe renal failure (creatinine clearance < 30 ml / min), liver failure, chronic alcoholism, anorexia, bulimia, cachexia, hypovolemia, dehydration, deficiency of glucose-6-phosphate dehydrogenase.

Posology and administration

Average single dose of the product depends on the child's body weight and is **10-15 mg/kg** of body weight. Maximum daily dose shall not exceed **60 mg/kg** of body weight. Minimum interval between doses of the product shall be 4 hours. For convenience and accuracy of dosing, it is necessary to use a measuring spoon supplied with the product. The product can be given to the patient both without dilution, and after dilution (with water, milk or juice).

The product is prescribed only with febrile temperature ($\geq 38.5^{\circ}\text{C}$) once per set dose. The next intake of the product is possible no earlier than at 4-6 hours, subject to the presence of febrile temperature.

Side effect

Diarrhea, abdominal pain, nausea, vomiting, tenesmus, decreased or increased prothrombin index and the international normalized ratio (INR), blood pressure reduction (as anaphylaxis symptom), thrombocytopenia, leukopenia, neutropenia, allergic skin and subcutaneous tissue reactions (skin rash, pruritus, urticaria, angioedema, anaphylactic shock, acute generalised exanthematous pustulosis, Stevens-Johnson syndrome, toxic epidermal necrolysis) are possible.

Overdose

In case of overdose, intoxication is possible, especially in children, patients with liver diseases (caused by chronic alcoholism), in patients with malnutrition, as well as in patients taking inducers of microsomal liver enzymes, in which fulminant hepatitis, hepatic insufficiency, cholestatic hepatitis can develop, cytolytic hepatitis, in the above cases - sometimes fatal.

The clinical picture of acute overdose develops within 24 hours after taking paracetamol.

Symptoms: gastrointestinal disorders (nausea, vomiting, loss of appetite, feeling of abdominal discomfort and / or abdominal pain), skin pallor. With simultaneous use in adults of 7.5 g or more or in children of over 140 mg/kg, cytolysis of hepatocytes occurs with complete and irreversible liver necrosis, development of liver failure, metabolic acidosis and encephalopathy, which can lead to coma and death. 12-48 hours after intake of paracetamol, there is an increase in the activity of "hepatic" transaminases, lactate dehydrogenase, bilirubin concentration and a decrease in the content of prothrombin.

Clinical symptoms of liver damage occur 1–2 days after drug overdose and reach a maximum of 3–4 days.

Treatment:

- Immediate hospitalization;
- Assay of blood plasma paracetamol before starting treatment at the earliest possible time after an overdose;
- Introduction of SH-group donors and precursors of the synthesis of glutathione - methionine and acetylcysteine within 10 hours after an overdose. The need for additional therapeutic measures (further introduction of methionine, intravenous introduction of acetylcysteine) is determined depending on the blood paracetamol concentration, as well as the time elapsed after its introduction;
- Symptomatic treatment;
- Liver function tests should be performed at the beginning of treatment and then - every 24 hours. In most cases, the activity of hepatic transaminases is normalized within 1 -2 weeks.

In very severe cases, a liver transplant may be required.

Interaction with other drugs

Phenytoin reduces the efficacy of paracetamol and increases the risk of hematotoxicity. Patients taking phenytoin should avoid frequent use of paracetamol, especially in high doses.

Probenecid almost twice reduces paracetamol clearance, inhibiting the process of its conjugation with glucuronic acid. In case of simultaneous prescription paracetamol dose reduction should be considered.

Care should be taken when using paracetamol and liver microsomal enzyme inducers (eg, ethanol, barbiturates, isoniazid, rifampicin, carbamazepine, anticoagulants, zidovudine, amoxicillin + clavulanic acid, phenylbutazone, tricyclic antidepressants).

Prolonged use of barbiturates reduces the efficacy of paracetamol. Salicylamide increases the half-life of paracetamol.

The INR should be monitored during and after the end of simultaneous use of paracetamol (especially in high doses and / or for a long time) and coumarins (for example, warfarin), since paracetamol when taken in a dose of 4 g for at least 4 days may enhance the effects of indirect anticoagulants.

Effects on ability to drive and use machines.

Effects on ability to drive and use machines have not been studied. If a patient experiences dizziness, psychomotor agitation and disorientation of orientation in space and time, he is not recommended to drive a car and other mechanisms during treatment with the drug.

9.4 Methods for monitoring compliance with procedures

Compliance of the study product / placebo (adherence to therapy) will be assessed at Visits 2 and 3 according to the patient's electronic diary by checking the data entered by the patient's parent about taking the drug.

On Visit 1, one bottle of the prescribed drug will be given to the patient's parent / adoptive parent.

At Visit 3, the vial of the prescribed drug must be returned by the patient's parent / adoptive parent to the study center.

Monitoring compliance with the protocol procedures during the study is carried out by the investigator

According to the draft Patient information leaflet for Polyoxidonium, during therapy, patients from 1 to 2 years should receive the drug by 1 injection x 2 times per day sublingual (14 drugs in total / 14 doses), patients from 2 to 5 years - intranasal 1 injection in each nasal passage x 2 times a day (14 applications total / 28 doses), patients from 5 to 8 years old - intranasal 1 injection in each nasal passage 3 times a day (21 applications total / 42 doses), patients from 8 to 12 years old - intranasal for 2 injections per each nasal passage 2 times a day (14 applications in total / 56 doses). Possible omissions of taking the drug during the study:

No more than two misses with 2-fold SP / placebo.

No more than four passes - with 3-fold use of SP / placebo.

These conditions will allow maintaining the level of compliance not lower than 80% [21 - 24].

If compliance is less than 80%, patient data will not be included in the efficacy analysis.

Dosage of antipyretic drugs will be assessed during the study according to the Patient's Diary - by checking the completed data by the patient's parent about taking the drug on visits 2 and 3.

On Visit 1, one vial of the prescribed antipyretic drug will be given to the patient's parent / adoptive parent.

On Visit 3, the vial of the prescribed antipyretic drug must be returned by the patient's parent / adoptive parent to the study site.

10. EFFICACY ASSESSMENT

In this study, the efficacy will be assessed based on the body temperature changes recorded in the patient's diaries at home by the parent / adoptive parent of the child; based on the Symptom Assessment Scale, IMOS scale, evaluation of the efficacy of the patient's parent / adoptive therapy, the number of cases of consumption of the antipyretic drug, the number of cases of dropout of patients due to the need to prescribe antibacterial drugs.

The multiplicity and rules for the use of these diagnostic scales are described in detail in the protocol section 9.2 "Diagnostic scales and Patient's diary".

Primary efficacy criterion:

- Fever duration period³ $\delta = -0.52$ days will be considered as a superiority cut-off level. Axillary body temperature level ≤ 36.9 °C confirmed by two consecutive measurements (morning-evening/evening-morning) will be considered as the end of fever.

Secondary efficacy criteria:

- The dynamics of intoxication symptoms by Days 3, 8 of treatment, assessed according to the Symptom Assessment Scale .
- Assessment of the ongoing therapy efficacy by a physician at the end of treatment course (IMOS scale) - complete recovery (0 points), significant improvement (1 point), minor to moderate improvement (2 points), unchanged (3 points), worsening (4 points).
- Assessment of the ongoing therapy efficacy by the patient's parent/adoptive patient (excellent, good, satisfactory, not efficient) - scores from 0 to 3.
- Number of cases of the antipyretic product (paracetamol) consumption for the entire study period.
- Number of patients' dropout patients due to the need to prescribe the antibacterial products.
- Number of patients (%) with body temperature normalization (presence of axillary body temperature ≤ 36.9 °C in two consecutive measurements (morning-evening/evening-morning) on Day 5 of therapy.
- Number of patients (%) with clinical pattern normalization on Day 5 of therapy according to the Symptom Assessment Scale (total ≤ 3 points).

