5.8 Criteria for diagnosis

Acute respiratory viral infection (ARVI) is an acute, local (in most cases) respiratory tract infection presenting with catarrhal inflammation of the upper respiratory tract and proceeding with fever, runny nose, sneezing, cough, sore throat, a violation of the general condition of different manifestations.

The patient or parents (legal representatives) may complain of acute rhinitis and / or cough and / or conjunctival hyperemia (catarrhal conjunctivitis) in combination with symptoms of rhinitis, pharyngitis. The disease usually begins acutely, often accompanied by an increase in body temperature to subfebrile values (37.5 °C — 38.0 °C). Febrile fever is more typical for influenza, adenovirus infection, and enterovirus infections. Elevated temperature in 82% of patients is reduced by the 2-3rd day of the disease; longer (up to 5-7 days) febrile is maintained during influenza and adenovirus infection [7]. An increase of fever intensity during the disease period, or appearance of severe intoxication symptoms may indicate the accession of a bacterial infection. Repeated raise of temperature after a short-term improvement often related to development of acute otitis media following the long-lasting runny nose.

Nasopharyngitis is characterized by complaints of nasal congestion, discharge from the nasal passages, nasopharynx discomfort: burning, tingling, dryness, often accumulation of mucous discharge, which in children, flowing down the posterior pharyngeal wall, can cause a productive cough. When inflammation spreads to the mucosa of auditory tubes (Eustachitis), clicking, noise and ear pain may occur, and a sense of hearing may decrease. Clinical course of nasopharyngitis has the following age features: in infants - fever, discharge from the nasal passages, sometimes - anxiety, difficulty in feeding and falling asleep. In older children, the typical manifestations are rhinitis symptoms (peak on day 3, duration up to 6-7 days), in 1 / 3-1 / 2 patients - sneezing and / or cough (peak on day 1, average duration - 6-8 days), rarely - headache (20% in the 1st and 15% - up to the 4th day) [8].

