9.1.4 Visit 3 (End of the treatment, Day 8 ± 1)

Visit 3 (End of the treatment, Day 8 ± 1) shall be held at the clinical center. The Investigator needs to conduct the following study procedures:

- Collection of patient's complaints;
- Physical examination;
- Measurement of major vital signs (HR, RR, body temperature)
- Symptom Assessment Scale completion

- Checking the diaries completion at home
- Adverse events registration
- Clinical blood test
- Common urine analysis
- Assessment of concomitant therapy
- Assessment of exclusion criteria
- Assessment of compliance with prescribed therapy
- Assessment of the ongoing therapy efficacy by a physician (IMOS scale)
- Assessment of the ongoing therapy efficacy by a parent/adoptive patient (IMOS scale)

On this visit, the patient shall return to the Investigator all the unused and used products. The Investigator shall calculate the returned product, including the antipyretic drug Efferalgan®, and fill in the appropriate form for accounting the study products.

The Investigator, on the basis of data obtained during this Visit, shall make a conclusion about the patient's condition.

If the patient has early terminated the study, he/she should undergo all the procedures provided for this Visit. Upon the completion of all the procedures of Visit 3, the Investigator shall inform the patient about the next visit - Visit 4 (Day 12 ± 1), which will be held through the telephone contact. For the visit, the study physician needs to determine a time convenient for the patient and/or the patient's parents/adoptive parents.

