9.1.5 Visit 4 (Study completion, Day 12 ± 1)

Visit 4 (Study completion, Day 12 ± 1) shall be held by telephone contact at a time convenient for the patient and/or parents/adoptive parents. The Investigator needs to conduct the following study procedures:

- Collection of patient's complaints
- Adverse events registration
- Assessment of concomitant therapy
- Study completion.

Upon the completion of all the procedures for Visit 4, the patient, as decided by the Investigator (in the absence of unresolved adverse events), completes the study.

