9.1.6. Description of study procedures

Demographic and anthropometric data collection

Demographic data include date of birth, age (number of full years at the time of participation in the study), gender and race. Anthropometric data include weight and height.

Medical history collection

The medical history data includes a description of the underlying disease, including the duration and effect of previously received therapy, a description of previous and concurrent diseases. In addition, information about concomitant therapy shall be collected: INN, trade name, strength, presentation, single and daily dose, date of therapy initiation and termination.

Physical examination

Physical examination includes an examination of the following organs and systems:

- Skin, hair, nails
- Endocrine system
- Cardiovascular system
- Respiratory system, state of nasal passages, character of discharge
- Gastrointestinal tract, including oral examination using a spatula and flashlight
- Nervous system
- Musculoskeletal system
- Reproductive system
- Urinary system

Measurement of vital signs

Measurement of HR, RR shall be performed by qualified medical personnel in accordance with the standards adopted at the study site.

The study is conducted as part of the safety assessment of study subjects.

Body temperature measurement.

It is conducted at screening visits, Visit 1, 2 and 3 by medical personnel, and at home by parents/adoptive patients.

Algorithm for measuring body temperature:

1. Wash your hands with warm water and soap
2. Inspect the armpit, and wipe it dry

3. Take a thermometer and shake off mercury below 35 °C
4. Position the thermometer in the armpit so that the measuring tank is in contact with the body from all sides
5. Measure the temperature for 10 min
6. Pay attention to between the body and the thermometer was no linen
7. Remove the thermometer and record the digital data
8. Shake the thermometer

Parents/adoptive parents should be instructed on how to conduct thermometry at Screening.

ECG

It shall be conducted at suspicion on cardiovascular disease. At least an hour before the procedure, it is necessary to exclude the outdoor games and emotional stress of the child. No less than 1.5 hours shall pass after the meal. In young children, special electrodes are used, which are tightly fixed on the skin without damaging it. Record at least 10–15 cardiac cycles, and if they are suspicion on of arrhythmia, there may be more cycles.

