9.2 Diagnostic Scales and Patient's Diary

During the study, the patient's condition and the therapy efficacy will be evaluated using the following parameters: 1) "Symptom Assessment Scale" (Appendix 1) - completed by the physician, 2) IMOS scale completed by the physician (Appendix 2) and also by the parent / adoptive parent (Appendix 3).

Symptom Assessment Scale completion will be conducted on Visit 0, Visit 1, Visit 2 and Visit 3. Also, on Day 5 of therapy, in the patient's diary the Symptom Assessment Scale shall be filled in; this procedure will be performed by the parent/adoptive parent. IMOS scale completion (Appendix 3) and assessment of the ongoing therapy efficacy by the patient's parent/adoptive patient (excellent, good, satisfactory, not efficient) will be held on Visit 3.

In addition, parents / adoptive parents of patients will be given a diary to record the patient's body temperature (twice a day: morning and evening), the time of taking the study product / placebo, the time and amount of taking antipyretic (paracetamol) and other drugs and their dosage and method of taking patients' complaints.

The diary and the diagnostic scales completed by the physician are the primary documentation; upon completion of the examination by the patients, they should be collected and kept together with the patient's medical record. When using electronic diaries, the data downloaded from them will be stored in the Investigator's file.

When conducting Visit 1 procedures, the Investigator must train the parents / adoptive parent to fill out a diary. At each visit, the Investigator must verify the correctness and timeliness of filling the diary with the patient's parent / adoptive parent.

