12.6 Procedures with missing/incorrect data

In this study, absent/missing data will not be completed.

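### A fever not confirmed as ended by Visit 3 has no defined duration: the last diary day is unstated, the sections disagree about Visit 4, and there is no rule for such a child

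*Combined protocol and SAP*

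**What the plan says.** **Endpoint.** Section 10 (also Section 7.1 and the synopsis) ends the fever when a temperature of at most 36.9 °C is "confirmed by two consecutive measurements (morning-evening/evening-morning) will be considered as the end of fever". Until that pair is seen, no duration is defined.

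**Readings.** Section 9.1.6 says of temperature measurement: "It is conducted at screening visits, Visit 1, 2 and 3 by medical personnel, and at home by parents/adoptive patients". Under Section 9.2 parents receive "a diary to record the patient's body temperature (twice a day: morning and evening"). Neither section names the last diary day.

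**Last scheduled check.** Section 9.1.4: "Visit 3 (End of the treatment, Day 8 ± 1) shall be held at the clinical center". Appendix 5 marks vital signs and diary checks up to this visit and not beyond. Visit 4 "shall be held by telephone contact at a time convenient for the patient and/or parents/adoptive parents"; its list in Section 9.1.5 covers complaints, adverse events and concomitant therapy, with no temperature and no diary.

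**Text pointing the other way.** Section 9.2 asks the investigator to verify the diary at each visit. Section 9.1 counts Visit 4 among the five visits and gives it the purpose of monitoring efficacy as well as safety. Sections 9.2 and 9.4 mention an electronic diary.

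**Analysis.** Section 12.6: "In this study, absent/missing data will not be completed"; Section 12.2 says the same. Efficacy is analysed in per-protocol completers. Section 12.3 declares success if the upper 95% confidence limit for the difference in mean duration is below −0.52 days. No censoring rule, assigned value or time-to-event method appears.

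**The concern.** A child whose last reading at Visit 3 is above 36.9 °C, or who has only one reading at or below it, can complete every scheduled procedure, stay in the per-protocol set and still have no primary value. The value is absent because the fever was long, so the loss depends on the outcome.

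The plan leaves two ways to handle such a child, and both bias the arm mean downward. Leaving the child out removes the longest durations. Entering the last reading as the end of fever understates the duration. The arm with more long fevers is affected more. The success rule leaves little room, because the planned effect and the margin are only 0.08 days apart.

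**Working it through.** **1. The plan's own figure.** Section 12.1 uses means of 2.6 and 3.2 days, SD 0.2, δ = −0.52, Zα = 1.645 and Zβ = 0.842.

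n = (1.645 + 0.842)² × 2 × 0.2² / (2.6 − 3.2 + 0.52)² = 77.3, rounded up to 78 per group. This reproduces. The gap that matters here is 0.60 − 0.52 = 0.08 days.

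**2. How much one lost child counts.** Take 78 children with true mean 3.2 and drop k children of duration d. The arm mean falls by k(d − 3.2)/(78 − k). The range of d is an assumption.

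| k | d = 7.5 | d = 8.5 |
|---|---|---|
| 1 | 0.056 | 0.069 |
| 2 | 0.113 | 0.139 |
| 4 | 0.232 | 0.286 |

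This shows sensitivity only. It does not say how many children would be lost.

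**3. How many might be lost.** Durations were given means 2.6 and 3.2, the same SD and distribution type in both arms, and normal, gamma or lognormal shape. Everyone beyond a cut-off was dropped. A 7-day cut-off corresponds to Visit 3 on Day 8 if time runs from Day 1; Day 7 and Day 9 give 6 and 8 days.

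SD 0.2 is the plan's figure. SD 1.4 is what follows if the earlier study's ± 0.2 were a standard error: 0.2√52 = 1.44 and 0.2√46 = 1.36. SDs of 2.0 and 2.5 are further assumptions.

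Results at 7 days, for a true difference of −0.60 (ranges are over the three shapes):

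| SD | Unresolved of 86, product / placebo | Difference if dropped | Shift | Difference if kept at 7 days |
|---|---|---|---|---|
| 0.2 | 0 / 0 | −0.60 | 0 | −0.60 |
| 1.4 | 0–1 / 0–2 | −0.58 to −0.59 | 0.01–0.02 | about −0.60 |
| 2.0 | 1–3 / 2–4 | −0.54 to −0.55 | 0.05–0.06 | about −0.59 |
| 2.5 | 3–5 / 6–7 | −0.485 to −0.53 | 0.07–0.115 | about −0.57 |

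The largest 7-day shift comes from the normal shape, where a truncated mean is μ − σφ(z)/Φ(z) with z = (7 − μ)/σ:

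- product: z = 1.76, mean 2.379
- placebo: z = 1.52, mean 2.864
- difference −0.485, shift 0.600 − 0.485 = 0.115

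That shape puts Φ(−2.6/2.5) = 15% of the product arm below zero days, so it is an outer bound. The gamma and lognormal shapes at SD 2.5 give 0.07 to 0.08.

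**4. Visit window.** If every child were seen on Day 7 (6-day cut-off), the shifts would be 0.04–0.05, 0.08–0.13 and 0.11–0.18 days at SD 1.4, 2.0 and 2.5. If every child were seen on Day 9 (8-day cut-off), they would be at most 0.01, about 0.02, and 0.04–0.06.

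**The case against.** A reader might infer that temperature readings stop at Visit 3. The documents do not say so. No sentence ends the home diary there, Section 9.2 calls for a diary check at each visit, Section 9.1 gives Visit 4 an efficacy role, and an electronic diary would make a remote check feasible. What stands is that these sections disagree with Section 9.1.5 and Appendix 5, which list no temperature or diary item for Visit 4.

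A reader might also infer that the plan orders the longest fevers out of the mean. It does not. Section 12.6 covers absent data without saying that a child with a full set of febrile readings counts as absent, and Section 12 defers final methods to a fuller analysis plan. Dropping is the most direct reading, not a written rule. A later plan could add a rule but could not recover readings that were never collected.

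On frequency, Section 5.8 expects temperature to fall by day 2–3 of illness in 82% of patients. It says "longer (up to 5-7 days) febrile is maintained during influenza and adenovirus infection". Influenza is excluded by test, and enrolment is within 24 hours of onset, so illness day 7 falls at or before about study Day 7. An unresolved fever at a nominal Day 8 visit therefore needs an early visit or a low-grade tail above 36.9 °C. This stands, and it keeps the expected number small. It does not bring it to zero: adenovirus is not screened out, and persisting fever is not an exclusion criterion. Nor can SD 0.2 be relied on to rule such children out, since a 5-day fever would lie (5 − 3.2)/0.2 = 9 SD above the placebo mean, which does not fit Section 5.8.

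Finally, every equal-shape scenario shrinks the effect, which is conservative for a superiority claim. That is fair for those scenarios. Overstatement would need more long fevers on the study product, which they do not cover. The ±1 day window applies to both arms alike, so by itself it adds noise and not bias.

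**Conclusion.** The point holds as a gap in the endpoint and an inconsistency about Visit 4. A child without a confirmed end of fever by Visit 3 has no defined duration, the sections disagree on whether the diary is still followed at Visit 4, and the plan has no rule for that child.

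The size is probably small, and the documents do not give the share affected. With a 7-day cut-off the shift passes the 0.08-day gap only at an assumed SD of about 2.5, and then only under the normal shape. At SD 2.0 it would take Visit 3 falling on Day 7 throughout. The bias is toward no effect if both arms have the same shape, but its direction in the trial is not guaranteed.

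It would be tempting to conclude from the two-child calculation that the primary result is undermined. The documents do not support that: a difference of two such children between arms is a chosen scenario, not a forecast. The change is still worth making before enrolment, because it affects which data are collected.

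**What to change.** **Data collection (Sections 9.1.5, 9.2 and Appendix 5).** Reconcile these with Section 9.1. State that morning and evening diary readings continue until the end-of-fever rule is met or until Visit 4, whichever comes first, and that Visit 4 records the outstanding readings.

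**Analysis (Sections 12.3 and 12.6).** State that a child without a confirmed end of fever at the last reading is not missing. The child enters the primary comparison of means with the duration to the last reading. A mean cannot treat that value as a minimum, so add a sensitivity analysis that treats it as right-censored, for example restricted mean time to a fixed day, or Kaplan-Meier curves with a log-rank test. Keeping such children at a 7-day cut-off already recovers most of the loss (−0.57 to −0.60 in the scenarios above), and the longer diary should leave fewer of them unresolved.

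**Cost.** Protocol wording, one extra CRF line at Visit 4, and a few more diary days for a few children. The drawback is that readings after Visit 3 come by telephone or electronic diary and are not checked in person.
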